6.1.6. Medical History

Medical history will be recorded at screening and will be reviewed at baseline to ensure no changes have occurred since the screening visit. Clinically relevant findings that are present prior to study drug initiation must be recorded on the Medical History page in the eCRF. Clinically relevant findings found after study drug initiation and meeting the definition of an AE (new AE or worsening of previously existing condition) must be recorded on the AE page in the eCRF.

FSHD-specific history will be recorded at screening.

6.1.7. Vital Signs

Vital sign (pulse rate, respiration rate, blood pressure, and temperature) assessments will be performed at the time points specified in [Table 7](#) and [Table 8](#). Assessments will be taken after the patient has been seated or recumbent for at least 5 minutes and before any 12-lead ECG assessment or blood sampling is performed.

6.1.8. Physical Examinations

Physical examinations will be performed at the time points specified in [Table 7](#) and [Table 8](#).

Physical examinations at screening and safety follow-up will include an evaluation of body systems, including but not limited to the following: skin; head, eyes, ears, nose, and throat; respiratory system; cardiovascular system; abdomen (liver, spleen); lymph nodes; neurological system; and musculoskeletal system.

Symptom-directed physical examinations can occur at any time during the study if triggered by AEs or if deemed necessary by the Investigator.

Weight (kg) will be recorded at screening and throughout the study at the time points specified in [Table 7](#) and [Table 8](#).

Height (cm) will be recorded and body mass index (BMI) calculated at screening: $BMI \text{ (kg/m}^2\text{)} = \text{weight (kg)} / (\text{height [cm]} / 100)^2$. Weight and height will be measured with shoes off and preferably with the same balance at each visit.

6.1.9. Twelve-Lead Electrocardiograms

Single 12-lead ECGs will be performed at the time points specified in [Table 7](#) and [Table 8](#). The primary ECG tracings will be locally read by the Investigator.

Twelve-lead ECGs will be performed after patients have been recumbent for at least 5 minutes. The ECGs should be performed after the measurement of vital signs and before any procedures that may affect heart rate (eg, blood sampling).

At the screening visit, if QTcF exceeds 450 msec for males or 470 msec for females, the ECG will be repeated 2 more times, and the average of the 3 QTcF values will be used to determine the patient's eligibility for the study.

Any clinically significant changes from baseline should be reported as AEs or SAEs, if applicable.

6.2. OTHER ASSESSMENTS

Assessments, described below, will be performed in Part A. [REDACTED]

[REDACTED] will also be performed in Part B.

6.2.1. Genetic Confirmation of FSHD

Genetic testing for FSHD is highly sensitive and specific. The finding of a D4Z4 contraction on chromosome 4q35 likely has a sensitivity of 93% and a specificity of 98% for the diagnosis of clinically defined FSHD. Healthy individuals possess at least 11 D4Z4 repeats, yielding a DNA fragment >38 kb on standard genetic testing. Affected individuals possess between 1 and 10 repeats, yielding DNA fragments ranging from 10 to 38 kb in size. Measurement of the size of the residual D4Z4 sequence on 4q35 forms the basis for genetic testing in FSHD ([Tawil et al.](#)

[figure not shown]
2015). For this study, only patients with 1 to 9 repeats will be enrolled. The number of repeats will be calculated by a diagnostic laboratory using the size of the D4Z4 bands on Southern blot testing. The site will enter the number of repeats into the IRT system. Patients with >9 repeats will be excluded from the study because such individuals tend to have slower progression and are more variable due to the presence of genetic modifiers.

[figure not shown]
FSHD2 (5% of FSHD) is also the result of hypomethylation of the D4Z4 region of chromosome 4q35. However, in this case, hypomethylation is not associated with a D4Z4 contraction. About 80% of patients with FSHD2 have a separate mutation in SMCHD1 (structural maintenance of chromosomes flexible hinge domain 1), a hypermethylating enzyme with a normal role in X chromosome inactivation. Mutations in SMCHD1 (and presumably other yet-to-be-defined loci) result in hypomethylation of the D4Z4 region, which leads to DUX4 transcript expression.

Genetic confirmation must be obtained before the patient is randomized. Genetic confirmation can come from previous testing, if verified with appropriate documentation from an accredited laboratory. If genetic testing is necessary, the [REDACTED] screening window and activities will not start until the results are obtained and verified by the Principal Investigator (PI).

Due to the stable transmission of repeat sizes within families, patients with a clinical diagnosis of FSHD who have a first-degree relative with a genetically confirmed diagnosis of FSHD may be entered into the study for screening assessments including MRI. During screening, a confirmatory genetic diagnosis will be conducted. If genetic testing during screening is necessary, the [REDACTED] screening window will not start until the results are obtained and verified by the PI.

[figure not shown]
Further detailed handling, processing, storage, and shipping procedures for genetic testing samples are described in a laboratory manual.

[figure not shown]
6.2.5. Patient Global Impression of Change

The PGIC will be performed at the visits noted in [Table 7](#) to obtain the patients' rating of overall improvement. Patients will be asked to rate their overall status at the start of the study on a scale from 1 (very much improved) to 7 (very much worse). The PGIC scale has been validated in several other indications and is recommended by the FDA for use as a meaningful measure of within-patient change ([Gautschi et al. 2016](#); [Chan et al. 2020](#)).

6.2.8. Neuro-QoL Upper Extremity Patient Reported Outcome

The Neuro-QoL UE function measure will be performed at the visits noted in [Table 7](#) to obtain the patients' self-reported rating of quality of life related to upper extremity function ([Cella et al. 2012](#)). The Neuro-QoL UE measures ability across fine motor and activities of daily living involving digital, manual and reach-related function and self-care. Responses are divided into 5 ordinal levels (1 = unable to do, 2 = with much difficulty, 3 = with some difficulty, 4 = with a little difficulty, 5 = without any difficulty).

6.2.12. Qualitative Exit Interview

A qualitative exit interview will be conducted in a subset of the patient population at Week 48 as noted in [Table 7](#) to assess the patient's experience during the study.

The purpose of the qualitative exit interview is to capture study participants' subjective experience with treatment, with study participation, and to gather insights to inform interpretation and clinical meaningfulness of the primary endpoint, RWS. Interview topics will include their experience with the disease, associated symptoms, symptom impact/burden and interference on the patient's life, patient perceptions of meaningful changes during the double-blind treatment period, and to explore patient experience with treatment.

The interview will consist of a 1-time telephone interview, lasting approximately 60 minutes. Interviews will be conducted by trained interviewers using a semi-structured interview guide and will be conducted within 7 days of completing the Week 48 visit. Neither failure to complete the interview nor completion outside of the targeted 7-day window will constitute a protocol deviation. All patients enrolling in the study will be invited to participate in the qualitative interview until the targeted subsample of at least 60 patients has been filled. This sample is large enough to accomplish objectives and reasonable for achieving a mix of patients from each treatment arm as well as inclusion of a small number of the patients who will be enrolled with FSHD2. If more study participants are consented than required, the larger pool of interview candidates will be used to select a more diverse sample across countries and/or regions.

[figure not shown]
Patients will be invited to participate in the qualitative interview substudy as part of the main consenting process at the beginning of the study. Patients already enrolled and randomized at the time of this amendment can be invited later in their treatment period and can re-sign the amended consent form to document their willingness to participate in the substudy. Patients who agree to

participate in the qualitative exit interviews will also be asked to complete a contact information transfer form during the consent process, which gives the clinic site staff permission to provide their contact information to the interview team and allows the interviewers in each country to contact the patients directly to schedule their interview at a convenient date and time.

Additionally, the clinic site staff will obtain verbal consent no later than the Week 48 visit (Visit 6) to confirm that the patients are still willing to participate in the exit interview sub-study.

Fulcrum has engaged Evidera Patient Centered Research to support the study by providing skilled interview services. Before conducting the interview, Evidera will confirm with the site that the study participant has completed the necessary study procedures for the Week 48 visit to ensure compliance with the exit interview protocol procedures. Evidera personnel are not authorized to contact patients after they complete their exit interview.

Any unfavorable changes or AEs reported by the patients during the conduct of the exit interviews will be communicated to the Investigator or designee by the interviewer within 24 hours (or 1 business day). The Investigator will be responsible for reporting all AEs and SAEs based upon appropriate medical judgement in accordance with this protocol.

6.2.14. Sample Collections

Processing, storage, and shipping procedures for all clinical laboratory samples are provided in the laboratory manual.

7. ADVERSE EVENTS AND SERIOUS ADVERSE EVENTS

The Investigator is responsible for reporting all AEs that are observed or reported during the study regardless of their relationship to study drug or their clinical significance. All AEs from the time of Part A informed consent and assent, if applicable, through the last follow-up visit in Part A or Part B (if applicable) will be recorded in each enrolled patient's eCRF.

7.1. DEFINITIONS

7.1.1. Definition of Adverse Event

An AE is defined as any untoward medical occurrence in a patient or clinical investigation patient administered a pharmaceutical product and which does not necessarily have to have a causal relationship with this treatment. An AE can therefore be any unfavorable and unintended sign (including an abnormal laboratory finding, for example), symptom, or disease temporally associated with the use of a medicinal product, whether or not considered related to the medicinal product (International Council for Harmonisation [ICH]-E2A). Conditions that were already present at the time of informed consent should be recorded on the Medical History page of the eCRF. Adverse event monitoring should be continued for at least 30 days after the last dose of study drug.

Disease progression should not be regarded or reported as an AE itself, unless it is associated with a separate AE.

Patients will be instructed to contact the Investigator at any time after randomization if any symptoms develop.

7.1.2. Definition of Treatment-Emergent Adverse Event

A TEAE is defined as any event that was not present before exposure to the study drug or any event already present that worsens in either intensity or frequency after exposure to the study drug.

7.1.3. Definition of Serious Adverse Event

An SAE is defined as any event that meets 1 of the following criteria:

- results in death
- is immediately life-threatening
- requires inpatient hospitalization or prolongation of existing hospitalization
- results in persistent or significant disability/incapacity
- constitutes a congenital anomaly or birth defect

Important medical events that may not result in death, be life-threatening, or require hospitalization may be considered SAEs when, based upon appropriate medical judgment, they

may jeopardize the patient or may require medical or surgical intervention to prevent one of the outcomes listed in this definition. Examples of such medical events include allergic bronchospasm requiring intensive treatment in an emergency room or at home, blood dyscrasias or convulsions that do not result in inpatient hospitalization, or the development of drug dependency or drug abuse.

7.1.3.1. Definition of Terms

Life-threatening: Life-threatening means that the patient was at immediate risk of death from the event as it occurred; ie, it does not include a reaction that if it had occurred in a more serious form might have caused death. For example, drug-induced hepatitis that resolved without evidence of hepatic failure would not be considered life-threatening even though drug induced hepatitis can be fatal.

Hospitalization: AEs requiring in-patient hospitalization or prolongation of an existing hospitalization should be considered SAEs. Hospitalization for elective surgery or routine clinical procedures that are not the result of AE (eg, elective surgery for a pre-existing condition that has not worsened) need not be considered AEs or SAEs. If anything untoward is reported during the procedure, that occurrence must be reported as an AE, either “serious” or “non-serious” according to the usual criteria.

In general, hospitalization signifies that the patient has been detained (usually involving at least an overnight stay) at the hospital or emergency ward for observation and/or treatment that would not have been appropriate in the physician's office or outpatient setting. When in doubt as to whether “hospitalization” occurred or was necessary, the AE should be considered serious.

Disability/incapacitating: An AE is incapacitating or disabling if the experience results in a substantial and/or permanent disruption of the patient's ability to carry out normal life functions.

7.1.4. Definition of Suspected Unexpected Serious Adverse Reaction

A suspected unexpected serious adverse reaction (SUSAR) is defined as an untoward and unintended response to a study drug, which is not listed in the applicable product information, and meets one of the following serious criteria: results in death, is life-threatening, requires hospitalization or prolongation of an existing hospitalization, results in persistent or significant disability or incapacity, or is a congenital anomaly or birth defect.

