7.1.5. Reference Safety Information

No serious adverse reactions are considered expected by the Sponsor for the purpose of expedited reporting of SUSARs and identification of SUSARs in the “Cumulative summary tabulations of serious adverse reactions” section of the current Investigator's Brochure for the investigational medical product.

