7.5. ADVERSE EVENTS OF SPECIAL INTEREST

An AESI (serious or non-serious) is one of scientific and medical concern for which ongoing monitoring and rapid communication by the Investigator to the Sponsor is appropriate. If an AE or the abnormality is an AESI, the event should be reported on an SAE form, regardless of seriousness, and captured in the safety database. Non-serious AESIs will not be reported to the Regulatory Authorities unless required.

Adverse events of special interest for this study include liver tests that meet the criteria for potential drug-induced liver injury, in accordance with the US FDA "Guidance for Industry-Drug-Induced Liver Injury: Premarketing Clinical Evaluation."

Liver Tests and Stopping Criteria

The following 3 laboratory value criteria must be met for potential DILI, or "Hy's Law":

- An elevated ALT or aspartate aminotransferase laboratory value that is $\geq 3 \times$ ULN
- An elevated total bilirubin laboratory value that is $\geq 2 \times$ ULN
- An alkaline phosphatase laboratory value that is $< 2 \times$ ULN

Study drug should be discontinued for patients who meet the laboratory criteria for potential DILI as a result of within-protocol specific testing or unscheduled testing. This AESI must be reported to the Sponsor within 24 hours of awareness. Further safety steps should be taken to closely observe and follow the event until resolution. These steps include, but are not limited to:

- Making every reasonable attempt to have the patient return to the clinic within 24 hours for repeat liver enzyme tests.
- Obtaining a more detailed history of symptoms and prior or concurrent disease, concomitant medication use, alcohol use, recreational drug use, and special diets.
- Repeating liver enzyme and serum bilirubin tests twice weekly. Frequency of retesting can decrease to once a week or less if abnormalities stabilize and the patient is asymptomatic.
- Obtaining viral hepatitis serology.
- Considering liver imaging and/or hepatology consultation.

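### The protocol's SUSAR definition (7.1.4) omits the important-medical-event criterion of its SAE definition (7.1.3), so a related, unexpected SAE that is serious only on that ground is not a SUSAR by the protocol's own rule

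*Protocol*

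**What the plan says.** **SAE (Protocol 7.1.3).** Five outcomes make an event serious: death, immediate threat to life, inpatient admission or a longer stay, disability, and birth defect. The section then adds a judgement-based route: "Important medical events that may not result in death, be life-threatening, or require hospitalization may be considered SAEs when, based upon appropriate medical judgment", the event may put the patient at risk or need intervention to prevent one of those outcomes. Its examples include blood dyscrasias and convulsions that do not lead to admission.

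**SUSAR (Protocol 7.1.4).** The reaction must be absent from the product information and must be one that "meets one of the following serious criteria: results in death, is life-threatening, requires hospitalization or prolongation of an existing hospitalization". The list ends with "results in persistent or significant disability or incapacity, or is a congenital anomaly or birth defect". There is no further item and no reference to 7.1.3.

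**Expectedness (Protocol 7.1.5).** "No serious adverse reactions are considered expected by the Sponsor" for the purpose of expedited SUSAR reporting.

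**Liver events (Protocol 7.5).** "Adverse events of special interest for this study include liver tests that meet the criteria for potential drug-induced liver injury". These go on an SAE form whether or not they are serious, enter the safety database, and must reach the Sponsor within 24 hours of awareness. As to onward reporting: "Non-serious AESIs will not be reported to the Regulatory Authorities unless required".

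**Onward reporting (Protocol 7.3.2 and 7.3.4).** SUSARs go unblinded to authorities and ethics committees on the timelines those authorities set, and blinded to investigators. The Sponsor also undertakes to comply with each country's safety-reporting requirements.

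**The concern.** A SUSAR is a serious event that is also suspected to be drug-related and unexpected. The seriousness test should therefore be the same for both terms. Here the protocol sets out two tests, and the SUSAR one is shorter.

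The difference matters more because of 7.1.5. If no serious reaction is expected, expectedness screens nothing out. For an SAE already suspected to be drug-related, the list in 7.1.4 is then the only remaining filter, and it removes one class of SAE.

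The trial's named event of special interest can fall into that class. Hepatotoxicity is the first potential risk described (1.3.2.1). The follow-up steps in 7.5 rest on a return to the clinic and repeat blood tests, so the protocol foresees cases managed without admission. What is at stake is whether the protocol's own definition classes such a case, once judged serious and related, as a SUSAR and so sends it to authorities, ethics committees and investigators under 7.3.4.

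**Working it through.** The documents give no figure to reproduce, so the check compares text.

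**Step 1. The two lists side by side.**

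| Route to seriousness | SAE, 7.1.3 | SUSAR, 7.1.4 |
|---|---|---|
| Death | yes | yes |
| Threat to life | yes | yes |
| Admission or longer stay | yes | yes |
| Disability | yes | yes |
| Birth defect | yes | yes |
| Important medical event, on medical judgement | yes | absent |

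Routes: 6 for an SAE and 5 for a SUSAR; 6 − 5 = 1 missing. The sentence in 7.1.4 is grammatically complete, with no sign of redaction or lost text at that point.

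**Step 2. Combine with 7.1.5.** No serious reaction is expected, so suspected relationship plus seriousness should be enough for a SUSAR. Under 7.1.4 they are enough for five routes and not for the sixth. The three sections do not fit together. A related convulsion without admission, of the kind 7.1.3 gives as an example, can be an SAE. If it meets none of the five outcomes, it is not a SUSAR.

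**Step 3. Trace an unhospitalised potential-DILI case.**

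- Death, admission, disability, birth defect: none, by construction.
- Threat to life: Section 7.1.3.1 says "drug-induced hepatitis that resolved without evidence of hepatic failure would not be considered life-threatening", so this route is closed for a case that resolves in that way.
- Important medical event: open under 7.1.3 if the case is judged to qualify, absent from 7.1.4.

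The case meets 0 of the 5 SUSAR criteria. It can still be an SAE by the sixth route.

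**Step 4. Which reporting steps are affected?** Site to Sponsor: none. Section 7.5 requires notice of the liver event within 24 hours whatever its seriousness, and 7.3.2 sets 24 hours for any SAE. Sponsor onward: the classification on which 7.3.4 depends is affected.

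**Step 5. Rough frequency.** Section 1.3.2.1 reports combined ALT and bilirubin elevation in 5 of 1724 losmapimod patients (5/1724 = 0.29%) and 4 of 1752 placebo patients (4/1752 = 0.23%) in an acute coronary syndrome study. If the losmapimod rate is assumed to carry over to the 115 patients on active drug in Part A, 115 × 5/1724 = 0.33 cases. If it is applied to all 230 patients, 230 × 5/1724 = 0.67. That population differs, the protocol names other likely contributors, and the laboratory criteria differ from those in 7.5 (which also admits AST and caps alkaline phosphatase). The figure therefore shows only the order of size: about one case or none, before asking whether it is related, unhospitalised and judged serious. Section 1.3.2.1 also reports no SAE or special-interest event relating to hepatotoxicity in the Sponsor's FSHD studies so far.

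**The case against.** The strongest reply is that this is a drafting slip with several backstops.

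- Section 7.5 asks for much more than a form: 24-hour notice, database entry, stopping of study drug, prompt repeat tests, a fuller history and viral serology.
- Sections 7.3.2 and 7.3.4 bind the Sponsor to the authorities' rules, and 7.5 leaves room for onward reports of non-serious liver events where required.
- The Sponsor reviews cumulative safety data monthly or as needed (13.1.1), and an independent committee reviews Part A data (9.1.6.10).
- The liver example needs three conditions at once: suspected relationship, no admission, and seriousness by the judgement-based route alone. Section 7.5 does not class the event as serious. When there is doubt about hospitalisation, 7.1.3.1 says to treat the event as serious.

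All of this stands, and it limits the point. A reader might infer that an outpatient Hy's-law case would get no expedited report, or that notice to authorities and other sites would be delayed. The documents do not support either reading. No section bars an onward report, reporting to the Sponsor is already expedited, and the external rules to which the protocol defers cannot be seen here.

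The reply does not remove the inconsistency. The reference to authorities' requirements in 7.3.4 governs how a SUSAR is reported, not what counts as one. The proviso in 7.5 concerns non-serious events, whereas the gap concerns serious ones. The commitment in 7.3.2 may lead the Sponsor to the right result, but only by setting aside the protocol's own definition.

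**Conclusion.** The point holds in a limited form. Sections 7.1.3, 7.1.4 and 7.1.5 are inconsistent: a suspected drug-related SAE whose only ground of seriousness is that it is an important medical event is not a SUSAR under the protocol's wording. A stated rule misclassifies these events, so this is more than missing detail.

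It is limited to one of six seriousness routes and to the Sponsor's onward classification, and few events are likely. No endpoint, estimand or efficacy analysis is touched. The SAP's SAE tables use the SAE classification recorded in the eCRF (SAP 9.3.4.1), so they do not change.

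The conclusion assumes that 7.1.4 is read literally as a closed list. The liver illustration also assumes that the case is judged serious as an important medical event and causally suspected; the protocol does not say that every potential-DILI case is either. The correction is worth making because it is cheap and because 7.1.5 leaves the seriousness list as the only filter once a relationship is suspected.

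**What to change.** In Protocol 7.1.4, replace the restated criteria with wording such as: *meets any seriousness criterion in Section 7.1.3, including important medical events*. That one cross-reference reconciles 7.1.4 with 7.1.3 and 7.1.5 and prevents the two lists from drifting apart again. Section 7.5 does not need rewriting for this purpose, since it does not contradict 7.1.3.

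The cost is one sentence in the next amendment. The downside is possibly a few more expedited reports.
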